12.7.5 Change from Baseline to Week 52/Termination in ALT (U/L)

This endpoint will be derived from the central laboratory dataset. Analysis will include data obtained until Week 52/Termination. The Full Analysis Set (FAS) will be used for the analysis of this endpoint.

The statistical model will be a Mixed Model for Repeated Measures (MMRM) (SAS[®] MIXED procedure with REPEATED sub-command). The model will include the following fixed effects: categorical week in trial by treatment interaction, CGR₁ and baseline ALT value (1df). The model will use the unstructured covariance structure and the REML estimation method and degrees of freedom will be adjusted using the Kenward-Roger method. Data from all changes form baseline to scheduled post-baseline visits will be used as response in the model and differences between the treatments groups at Week 52/Termination will be estimated using contrasts.

Protocol No: 005 ARREST study

In case that the model will not converge, the Maximum-Likelihood (ML) estimation method will be used instead of the default Restricted ML (REML). If the model still does not converge, then a simpler covariance structure with less parameters will be used, according to the following order: Heterogeneous Autoregressive(1) [ARH(1)], Heterogeneous Compound Symmetry (CSH), Autoregressive(1) [AR(1)], and Compound Symmetry (CS).

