4.3.5 Key Secondary Endpoints

- 1. Proportion (%) of subjects with CRN fibrosis score improvement
- 2. Proportion (%) of subjects with NAS score improvement without worsening of CRN fibrosis score..
- 3. Proportion (%) of subjects with SAF activity score improvement without worsening of CRN Fibrosis Score.
- 4. Proportion (%) of subjects with NASH resolution without worsening of CRN fibrosis score
- 5. Change from baseline to Week 52/Termination in ALT (U/L). level

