5 STUDY DESIGN

5.1 Over view and plan

This is a multicenter, phase IIb, randomized, double blind, placebo controlled study designed to evaluate the efficacy and safety of two Aramchol doses (400 mg and 600 mg) in subjects that

are 18 to 75 years of age, with Non-Alcoholic Steatohepatitis (NASH) and type II DM or elevated fasting glucose and overweight/obesity (type II diabetic or pre diabetic). Eligible subjects will be enrolled in three treatments arms:

- Aramchol 400 mg tablets
- Aramchol 600 mg tablets
- Placebo for Aramchol

The subjects will be evaluated at study sites for 11 scheduled visits: visit 1 (screening), visit 2 (baseline), visit 3 (2 weeks), visit 4 (4 weeks), visit 5 (8 weeks), visit 6 (12 weeks), visit 7 (24 weeks), visit 8 (32 weeks), visit 9 (40 weeks), visit 10 (End-of-Treatment/Early Termination) (52 weeks) and visit 11 (follow up) (65 weeks).

The subjects will be treated for a period of 52 weeks. After completion of the study treatment period, the subjects will be followed up for an additional period of 13 weeks without study medication

During the study the following assessments will be performed:

- Vital signs will be measured at each study visit.
- A physical examination will be performed at the screening visit, 24 weeks, End-of-Treatment/Early Termination and week 65 visits.
- The following safety blood tests will be performed: complete blood count (CBC), serum chemistry (including electrolytes, liver enzymes, direct and total bilirubin, glucose, lipid profile which include triglyceride, cholesterol, HDL, LDL and VLDL, CPK, creatinine, urea, albumin, alkaline phosphatase), ESR and during the screening visit, baseline, week 2, 4, 8, 24, 40, 52 and 65 (end of follow up) visits. Serology (HBV, HCV and HIV) and urinalysis will be performed during the screening visit. Coagulation (fibrinogen, PT/INR, aPTT) will be performed during the screening, baseline, week 24, End-of-Treatment/Early Termination and week 65 visits. Insulin (HOMA) will be measured in the screening, week 24 and End-of-Treatment/Early Termination visits. HbA1c will be measured in the screening, week 8, 24, 40 and End-of-Treatment/Early Termination visits. C reactive protein, Leptin, Adiponectin,

will be measured in baseline visit and end of treatment period (week 52, visit 10). The blood samples taken at these visits, will be tested for possible biomarkers

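### The Week 52 ALT model fixes one baseline slope for all visits; a baseline-by-week term would recover precision if correlation with baseline falls over time

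*Combined protocol and SAP*

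**What the plan says.** Section 4.3.5 defines the endpoint as "Change from baseline to Week 52/Termination in ALT (U/L"), so the unit is part of the definition. Section 12.7.5 sets out the model:

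- Fixed effects: "The model will include the following fixed effects: categorical week in trial by treatment interaction", followed by "CGR₁ and baseline ALT value (1df"). No baseline-by-week term is listed.
- Covariance: "The model will use the unstructured covariance structure and the REML estimation method", with Kenward-Roger degrees of freedom.
- Response: "Data from all changes form baseline to scheduled post-baseline visits will be used as response in the model". The contrast is taken at Week 52/Termination.
- Source: "This endpoint will be derived from the central laboratory dataset".

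Section 5.1 schedules chemistry at "baseline, week 2, 4, 8, 24, 40, 52 and 65 (end of follow up) visits". Week 65 falls outside the model, which leaves six possible post-baseline visits. Sections 8.2.4 and 10.2 and footnote 7 of Table 1 allow weeks 2, 4, 8 and 40 to be analysed locally or in a per-country laboratory. Of the interim visits with chemistry, Section 8.2.4 names only week 24 as tested in the central laboratory.

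Section 12.11 also lists change in ALT under an ANCOVA of change to end of study, adjusted for baseline.

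**The concern.** With equal variances over time, the slope of change on baseline at week t is the correlation of week-t ALT with baseline, minus 1. If that correlation falls during the year, the slope steepens. A model with one slope must compromise, and early visits, which track baseline closely, pull the compromise towards zero. The adjustment at Week 52 is then too small.

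Two things are at stake. The Week 52 contrast has more variance than the same data would give with a slope for each visit. And in a trial where the arms happen to differ in baseline ALT, the estimate keeps part of that difference. With 43 placebo subjects against 86 per dose, such a difference is a realistic prospect.

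**Working it through.** **The plan's own figures.** Section 12.1 gives 215 evaluable subjects (86, 86 and 43) and 240 in total. An assumed 10% loss fits this: 86/0.9 = 95.6 and 43/0.9 = 47.8, rounded up to 96 and 48. No power, SD, effect or correlation is given for ALT, so there is no ALT figure to reproduce. Only the arm sizes are used below.

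**Assumptions.** Equal variance at all visits; complete data; CGR1 ignored. The correlation between two visits depends on the gap between them and falls exponentially from r2 (2-week gap) to r52 (52-week gap): ρ(g) = r2·exp[−k(g − 2)], with k = ln(r2/r52)/50. Linear decay was run as a check.

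**Formulas.** Let β_t = ρ_t − 1, and let Σ be the covariance of the visits given baseline. Then:

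- Common slope in large samples: b = (1′Σ⁻¹β)/(1′Σ⁻¹1).
- Week 52 estimate: difference in mean change minus b times the difference in mean baseline.
- Extra variance relative to a slope per visit: (β₅₂ − b)²/(1 − ρ₅₂²), in units where the baseline variance is 1.
- Power, for a contrast with 80% under a slope per visit: Φ(2.802/√(1 + extra) − 1.960).

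**Two visits, checkable by hand (0.85 falling to 0.5).** k = 0.0106, ρ₂₄ = 0.673, ρ₅₂ = 0.500, and the week 24 to 52 correlation is 0.645. Given baseline, the variances are 0.547 and 0.750 and the covariance is 0.309. The weights are proportional to 0.750 − 0.309 = 0.441 and 0.547 − 0.309 = 0.238. So b = [0.441(−0.327) + 0.238(−0.500)]/0.679 = −0.388. The gap is 0.112 and the extra variance 0.112²/0.75 = 1.7%.

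**Six visits (weeks 2, 4, 8, 24, 40, 52), same decay.** β₅₂ = −0.50 and b = −0.215. The gap is 0.285 and the extra variance 0.285²/0.75 = 10.8%. Power is Φ(2.802/√1.108 − 1.960) = 75.8%.

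| r2 to r52 | Extra variance, six visits | Power (80% with fix) | Extra variance, weeks 24 and 52 only |
|---|---|---|---|
| 0.70 flat | 0% | 80.0% | 0% |
| 0.80 to 0.70 | 1.0% | 79.6% | 0.2% |
| 0.80 to 0.60 | 3.7% | 78.6% | 0.6% |
| 0.85 to 0.50 | 10.8% | 75.8% | 1.7% |
| 0.85 to 0.40 | 15.8% | 74.0% | 2.1% |
| 0.90 to 0.50 | 15.8% | 74.0% | 2.4% |
| 0.90 to 0.30 (extreme) | 28.5% | 69.6% | 2.7% |

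Linear decay raises these somewhat. Leaving out the extreme row, the largest values become 17.1% (six visits) and 3.7% (two visits). In the extreme row they become 31.2% and 6.5%.

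**Chance imbalance.** One standard error of the baseline difference is √(1/86 + 1/43) = 0.187 SD. With a gap of 0.285, 0.187 × 0.285 = 0.053 SD stays in the estimate. For scale, assume log-normal ALT with median 55 U/L and log-SD 0.40. The SD is then 55·e^0.08·√(e^0.16 − 1) ≈ 25 U/L, so about 1.3 U/L remains. A 20% reduction from 55 is 11 U/L.

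**Simulation (2,500 trials per scenario, 86 vs 43, log-normal ALT).** With six visits and 0.85 falling to 0.5, the Week 52 estimate moved by −0.25 to −0.30 per unit of imbalance under the common slope. With baseline-by-week it moved by about 0 (−0.02 to 0.05). Type I error was 3.5 to 5.5% under every model, and no average bias appeared under the null.

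**The case against.** The strongest reply is that the early visits may not be in the model at all. The endpoint uses the central laboratory dataset, and weeks 2, 4, 8 and 40 may be local. With only weeks 24 and 52, the loss nearly disappears. This stands, and it sets the lower end of the range. It does not settle the matter, because 12.7.5 also says that all scheduled changes are used.

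The size also rests wholly on assumed correlations, and a flat correlation gives no loss. That stands too.

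A reader might infer several stronger points that the documents do not support:

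- **The ALT test is biased or invalid.** Randomisation balances baseline on average, and type I error held. The error is conditional on a chance imbalance.
- **Analysing U/L leaves imbalance uncorrected.** It does not. In U/L with baseline-by-week the dependence on imbalance was near zero (−0.02 to 0.06). Skewness can cost power: with weeks 24 and 52 only, the 0.85 to 0.5 decay, log-SD 0.55 and a 20% effect, power was 61.2% as planned and 68.0% on the log scale. But the data were generated as log-normal, which favours the log model, and a log analysis turns a U/L endpoint into a ratio.
- **The fallback covariance is a material flaw.** The plan says "then a simpler covariance structure with less parameters will be used, according to the following order: Heterogeneous Autoregressive(1"). This treats unequally spaced visits as equally spaced, but applies only after the unstructured model has failed under both REML and ML.

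**Conclusion.** The point holds as a matter of efficiency. The single 1-df baseline term is a restriction that the rest of the model does not share, and it is too shallow at Week 52 whenever the correlation with baseline declines. The cost is nil with a flat correlation, about 1 to 17% extra variance with plausible decay over six visits, and about 0 to 4% if only weeks 24 and 52 contribute. An 80% contrast would fall to about 74 to 80% with six visits. Part of a chance imbalance also stays in the estimate: about 0.05 SD of baseline ALT for a one-standard-error imbalance in the worked six-visit case.

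Validity is not in question. ALT comes last in the testing order of Section 12.7, so the consequence for the trial's conclusions is limited. The change is worth making because it is cheap and leaves the endpoint alone.

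**What to change.** In Section 12.7.5, add a baseline ALT by week interaction to the fixed effects. Keep change in U/L at Week 52 as the endpoint and leave the contrast as it is. The cost is one line of text and up to 5 degrees of freedom with six visits (1 with two).

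Secondary and optional:

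- State which visits and which laboratories feed the model, since this decides how much the interaction can gain.
- Add a log-ALT sensitivity analysis, reported as a percent difference, beside the U/L result and not in its place.
- Reconcile 12.7.5 with the ALT ANCOVA in Section 12.11. An end-of-study ANCOVA has its own slope and would not meet this problem, so the plan should say which analysis governs. Sections 12 and 12.11 say that the signed SAP prevails, but not which of these two analyses it contains.

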12.9 Safety and Tolerability Analyses

Safety analyses will be performed for the Safety Analysis Set.

12.9.1 Adverse Events

An adverse event is any untoward medical occurrence in a patient administered a pharmaceutical product, regardless of whether it has a causal relationship with this treatment. In this study, any adverse event occurring after the clinical study patient has signed the informed consent form should be recorded and reported as an adverse event.

The MedDRA dictionary Version 19 will be used to standardize the terms used by the investigator to describe the Adverse Events (AEs).

The following analyses are pre-planned for adverse events:

- The incidence (no. of patients) and frequency (no. of events) of most frequent TEAEs (>5% of subjects in at least one study arm) by Preferred Term.
- The incidence (no. of patients) and frequency (no. of events) of TEAEs when broken down by SOC and by SOC and Preferred Term according to MedDRA dictionary.
- The incidence (no. of patients) and frequency (no. of events) of TEAEs started during the off-drug study follow-up period (from week 52 to week 65) when broken down by SOC and by SOC and Preferred Term according to MedDRA dictionary.
- The incidence (no. of patients) and frequency (no. of events) of TEAEs by MedDRA System Organ Class and Preferred Term in Subjects Early Terminated from Study/Treatment.
- The incidence (no. of patients) and frequency (no. of events) of serious TEAEs by MedDRA System Organ Class and Preferred Term, data listing as well as summary table of SAEs when broken down by study trimesters (90 days each).
- The incidence (no. of patients) and frequency (no. of events) of TEAEs when broken down by severity.
- The incidence (no. of patients) and frequency (no. of events) of TEAEs when broken down by relationship to study IP.

- The incidence (no. of patients) and frequency (no. of events) of TEAEs when broken down by action taken.
- The incidence (no. of patients) and frequency (no. of events) of TEAEs when broken down by event outcome.
- Adverse Events dictionary used to code Investigator's verbatim terms will also be provided. Individual subject listings of TEAEs and non-TEAEs.

12.9.2 Laboratory Data

Analyses of safety central laboratory data will be performed in the following manner:

• The below table displays the quantitative criteria used to define the potentially clinically significant (PCS) abnormal laboratory values. Measurements used in the analysis are those taken only at post randomization day visits. The incidence tables of PCS lab values as well as the individual subject listing will be provided. Please note that the denominator to be used for calculating percentages is the number of subjects with at least one post randomization day observation.

Test Group	Parameter	Lower Normal SI	Upper Normal SI	Lower PCS	Upper PCS
Chemistry	ALBUMIN (g/L)	32	55		<30g/l
Chemistry	ALK PHOS (U/L)	29	149		>2.5ULN
Chemistry	ALT (U/L)		45		>3ULN
Chemistry	AST (U/L)		41		>3ULN
Chemistry	CALCIUM (mmol/L)	2.14	2.62	<2mmol/l	>2.9mmol/l
Chemistry	CHOLESTEROL (mmol/L)	2.2	5.2		>7.75mmol/l
Chemistry	CPK (U/L)	26	145		>2.5ULN
Chemistry	CREATININE (umol/L)	31	106		>1.5ULN
Chemistry	GGT (U/L)	2	42		>2.5ULN
Chemistry	GLUCOSE, PLASMA (mmol/L)	3.9	6.9	<3.0mmol/l	>13.9mmol/l
Chemistry	POTASSIUM (mmol/L)	3.5	5.3	<3.5mmol/l	>5.5mmol/l
Chemistry	SODIUM (mmol/L)	135	148	<130mmol/l	>150mmol/l
Chemistry	TOTAL BILIRUBIN (umol/L)	2	21		>1.5ULN
Coagulation	APTT (secs)	22	35		>1.5ULN
Coagulation	INR	0.8	1.2		>1.5ULN
Hematology	HEMOGLOBIN (g/L)	113	156	<100g/l	
Hematology	PLATELETS (x10E9/L)	140	370	<75 x10e9 /L	
Hematology	WBC (x10E9/L)	3.5	10.5	<3.0 x 10e9 /L	>100 x 10e9 /L

Criteria for Potentially Clinically Significant Laboratory Values

ULN=upper limit of normal range.

• The incidence (no. of subjects) of abnormal values at any time after randomization day, calculated for subjects with normal values at baseline will be provided. Analysis will include, per tested parameter, those subjects with normal baseline and at least one post-randomization

day measurements. Summary table will display the number and relative percentage of subjects with at least one abnormal value (above upper and below the lower normal range) at any time post randomization days.

- Quantitative laboratory measurements were categorized with reference to the normal ranges as Low, Normal or High. Shift analysis of the categorical change form baseline to each scheduled visit and to the last observed value will be provided. Please note that the last measurement per visit will be used to represent subject's value in the analysis in case of sporadic repeated measurement within a visit.
- Box-Plots of measurements done, figures of mean values ±SEs of changes from baseline as well as descriptive statistics for all laboratory quantitative parameters and changes from baseline will be provided by scheduled visits and treatment groups. Please note that the last measurement per visit will be used to represent subject's value in the analysis in case of sporadic repeated measurement within a visit.
- Evaluation of Drug-Induced Serious Hepatotoxicity (eDISH, Drug Saf 2011; 34 (3): 1-10) was performed according to the following:
 - ✓ Pre-study drug administration data was not included in the analysis.
 - ✓ Max ALT was defined as the maximal value of all ALT assessments measured after randomization.
 - ✓ The maximal Bilirubin (Total) value taken for the scatter plot was selected among measurements taken at the same day or after the maximum ALT value was detected.

The eDISH figure, list of subjects with potential drug-induced serious hepatotoxicity according to this analysis, summary table of the incidence of subjects falling within each of the 4 quadrants will be provided. For subjects falling within the Cholestasis and Hy's Law

Quadrants an additional individual subjects listings will be generated displaying demographics, exposure and termination reason, concomitant drug use, adverse events and selected laboratory data.

• The distribution of maximal values of AST, ALT and total bilirubin at any time after randomization day in term of the upper normal range multiples will be provided for subjects with normal AST, ALT and total bilirubin at baseline.

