- 4. Will be conducted at selected sites in Mexico, USA, Europe and Hong Kong at visit 4 or 9.
- 5. Only if investigator thinks it is necessary
- 6. Coagulation = fibrinogen, PT/INR, aPTT.
- 7. Lab samples will be done locally at site or central lab per country.
- 8. ESR performed by site; according to the lab manual
- 9. Baseline test will be conducted before first dose is administrated. (If the Endothelial Function test was not done on Visit 2 or needs to be repeated due to unacceptable test data, it will be done at Visit 3 or at an Unscheduled Visit before Visit 3)
- 10. Serum sample for investigational test will be collected and kept frozen.
- 11. This sample can be collected at any visit during the study if it was not approved by the IRB prior to the baseline visit.

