8.2.4 Visits 3 (2 weeks); 4 (4 weeks); 5 (8 weeks); 6 (12 weeks); 7 (24 weeks); 8 (32 weeks) and 9 (40 weeks)

Please note that the patient should fast for 8-12 hours before attending the visit, where labs are drawn

Israel: Visits 3, 4, 5, 6, 7, 9

All other countries: Visits 3, 4, 5, 7, 9

- Physical examination, weight and waist circumference (only at visit 7 (24 weeks)).
 Vital signs including sitting blood pressure, heart rate, respiratory rate and body temperature.
- Concomitant medication.
- Adverse Events that occurred since the last visit will be recorded.
- Safety laboratory assessments: Chemistry, Hematology, ESR and Urinalysis (to be taken at visits 3 (2 weeks); 4 (4 weeks); 5 (8 weeks); 7 (24 week) and 9 (40 weeks). The laboratory samples will be analyzed locally at the site or in some countries in one central lab per the country. The samples collected at visit 7 will be tested in the central lab (CRL)
- HbA1c will be assessed at visits 5 (8 weeks), 7 (24 weeks) and 9 (40 weeks). The samples will be sent to the central lab.
- Blood sample for Coagulation only at visit 7.
- Blood Metabolomics blood tests only at visit 7.

- Blood samples for insulin (HOMA) only at visit 7.
- ECG (12 leads) evaluation will be performed only at visit 7.
- Lifestyle changes (including importance of diet and exercise in weight management. Life style Questionnaire (appendix E) may be used as a guideline, but is not mandatory.
- Study medication dispensing (with the exception of visit 3) after calling the IWRS to obtain medication kit number.
- Drug accountability.
- Blood samples for Aramchol trough blood level one sample will be taken at visits 4, 6, 7 & 9 in Israel. One sample will be taken on visit 4 or visit 9 at selected sites in Mexico, USA, Europe and Hong Kong. The patients will be asked to take the daily tablet at the clinic after blood sample are taken and to record the time.

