10.2 Safety Laboratory Evaluations

All laboratory testing will be performed by a central laboratory facility and/or affiliated laboratories which work under the central laboratory regulations and within its tests normal ranges. On visits 3, 4, 5 and 9 those tests can be performed at site's local lab or at a central lab. The lab manual should be referred to for specific instructions.

The following tests will be performed:

- Serum Chemistry
 - Fasting Plasma Glucose
 - Creatinine
 - Creatinine Clearance
 - Bilirubin (direct and total)
 - Urea
 - AST (SGOT)
 - ALT (SGPT)
 - GammaGT (GGT)
 - Lipid profile- once in the study either at screening or any other visit; 8-12 hours fasting is mandatory: Total cholesterol, LDL cholesterol, HDL cholesterol, VLDL and triglycerides.
 - Albumin
 - CPK
 - Alkaline Phosphatase
 - hs-CRP
- Electrolytes
 - Sodium
 - Potassium

Protocol No: 005 ARREST study

- Chloride
- Calcium
- Phosphorous
- Coagulation
 - Fibrinogen
 - PT/INR
 - aPTT
- Serology (only at screening)
 - HBV
 - HCV
 - HIV
- Hematology
 - Hemoglobin
 - MCV
 - Hematocrit
 - Red Blood Cells count (RBC)
 - White Blood Cells count + differential
 - Platelet count
 - Basophils
 - Eosinophils
 - Lymphocytes
 - Monocytes
 - Neutrophils
 - Large Unstained Cells
- Urinalysis
 - pH
 - Blood
 - Glucose
 - Ketones
 - Erythrocytes
 - Protein
 - Specific Gravity (USG)
 - Nitrite
 - Leukocytes
 - Bilirubin
 - Urobilinogen
- ESR

Measurement of Complete Blood Counts, INR and chemistry are in fact regarded as current clinical practice for fatty liver patients, and should therefore be collected and analysis performed by the Central Laboratory according to the Visit Schedules.

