The sponsor must be provided with a copy of the laboratory's certification, and a tabulation of the normal ranges for each parameter required. Additionally, if at any time a patient has laboratory parameters obtained from a different outside laboratory, the sponsor must be provided with a copy of the certification and a tabulation of the normal ranges for that laboratory. At any time during the study, abnormal laboratory parameters which are clinically relevant (e.g. require dose modification and/or interruption of study drug, lead to clinical symptoms or signs or require therapeutic intervention), whether specifically requested in the protocol or not, must be recorded on the appropriate Comment CRF page in addition to the appropriate laboratory CRF page. When abnormal laboratory values or test results constitute an adverse event (i.e., induces clinical signs/ symptoms or requires therapy) they must be recorded on the Adverse Events CRF.

When, in the opinion of the investigator, other clinical laboratory evaluations may be relevant for assessing the patient's status, they will be completed and entered into the database as appropriate.

Special tests:

- Total cholesterol, HDL cholesterol, LDL cholesterol and triglycerides will be specifically determined as probable safety parameters in this study, which affect lipid metabolism.
- See Section 9.11 for additional specialty test (Exploratory Laboratory tests and other Laboratory tests needed)

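### Section 12.9.2 limits the laboratory safety outputs to central-laboratory data, yet weeks 2, 4, 8 and 40 may be tested at a site's local laboratory, so early transient rises could be under-counted.

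*Combined protocol and SAP*

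**What the plan says.** Section 12.9.2 opens with "Analyses of safety central laboratory data will be performed in the following manner". Under that line come PCS incidence and its denominator, incidence of abnormality in subjects normal at baseline, shift tables, box plots and means, eDISH, and the distribution of maximum ALT, AST and total bilirubin. One fixed table of normal limits is printed.

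The visit plan sends part of the testing elsewhere:

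- Section 8.2.4, on visits 3 to 9: "The laboratory samples will be analyzed locally at the site or in some countries in one central lab per the country". Visit 7 (week 24) is reserved for the study's central laboratory.
- Table 1, note 7, for the samples at weeks 2, 4, 8 and 40: "Lab samples will be done locally at site or central lab per country".
- Section 10.2: "On visits 3, 4, 5 and 9 those tests can be performed at" the site's own laboratory or a central one.

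Section 10.2 is not uniform. It also says that all testing is done by "a central laboratory facility and/or affiliated laboratories which work under the central laboratory regulations and within its tests normal ranges", and that blood counts, INR and chemistry should be "collected and analysis performed by the Central Laboratory according to the Visit Schedules". For an outside laboratory, "the sponsor must be provided with a copy of the certification and a tabulation of the normal ranges for that laboratory". No sentence says whether site-local values enter the tables of section 12.9.2.

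**The concern.** Several of these outputs are described as covering the whole period after randomisation. If the opening line is applied as written, a local-laboratory site's results from weeks 2, 4, 8 and 40 are collected but not tabulated. A rise in ALT, AST, bilirubin or CPK that starts early and resolves before a central sample would then be missing from the PCS and maximum-value outputs, and an ALT rise from eDISH. Because eDISH takes bilirubin from the day of the ALT peak onwards, a lost ALT peak also moves the bilirubin window. A subject who leaves such a site before week 24 with no early-termination sample could drop out of the PCS denominator.

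The trial is meant to choose the safer and more effective of two doses, and these tables by arm are where a reader looks for a liver or muscle signal. Three of the four affected visits fall in the first eight weeks.

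**Working it through.** The plan gives no figure of its own on this point, so there is nothing to reproduce.

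**Inputs from the document.** On-treatment chemistry after baseline is at weeks 2, 4, 8, 24, 40 and 52 (section 5.1). The local option covers visits 3, 4, 5 and 9, which are weeks 2, 4, 8 and 40. Week 24 is central, and week 52 carries no local option. 240 subjects are randomised (section 6).

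**Assumptions, not in the document.** Share of subjects at local-laboratory sites *s*; duration of a rise *d*; onset even over weeks 0 to 52; proportion *r* of abnormal local results rechecked centrally one week later.

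**1. Visits.** 4 of 6 scheduled on-treatment visits (67%) may be non-central. With all six visits counted, the longest interval without a result is 16 weeks (week 8 to 24, and again 24 to 40). With weeks 24 and 52 only, it is 28 weeks, and the first scheduled value moves from week 2 to week 24.

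**2. Panels.** 240 × 6 = 1,440 in total, and 240 × 4 = 960 are eligible for local testing (67%). That is an upper bound with every site local. At *s* = 10%, 25% or 50% the number is 96 (7%), 240 (17%) or 480 (33%).

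**3. Rises seen at a local-laboratory site.** A rise is seen if a counted visit *t* falls between onset and onset + *d*. The probability is the total length covered by the intervals from max(0, *t* − *d*) to *t*, divided by 52.

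| Duration | All six visits | Weeks 24 and 52 only |
|---|---|---|
| 4 weeks | 20/52 = 38% | 8/52 = 15% |
| 8 weeks | 32/52 = 62% | 16/52 = 31% |
| 12 weeks | 44/52 = 85% | 24/52 = 46% |

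**4. Central rechecks.** Of the onset weeks seen only at local visits (12, 16 and 20 for the three durations), 10, 15 and 19 lead to a rise still present one week later. The probability becomes (8 + 10*r*)/52, (16 + 15*r*)/52 and (24 + 19*r*)/52.

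| Duration | *r* = 0 | *r* = 0.5 | *r* = 1 |
|---|---|---|---|
| 4 weeks | 15% | 25% | 35% |
| 8 weeks | 31% | 45% | 60% |
| 12 weeks | 46% | 64% | 83% |

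**5. Whole trial, no recheck.** The proportion seen is (1 − *s*) × all-visit value + *s* × central-only value. For *s* = 25% and 50% this gives 33% and 27% at 4 weeks, 54% and 46% at 8 weeks, and 75% and 65% at 12 weeks. With all results used, the values are 38%, 62% and 85%.

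**6. Early onset.** For a 4-week rise starting evenly in weeks 0 to 8, all results see 100%. Central values alone see 0% with no recheck, 44% with half rechecked and 88% with all rechecked.

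Week 65 adds nothing for these durations, because the latest end is 52 + 12 = 64. Early-termination samples and other unscheduled samples carry no local option and are not modelled. They could raise the central-only figures.

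**The case against.** The exclusion rests on one adjective in a lead-in. The bullets beneath it name no laboratory: the eDISH bullet takes the maximum over all ALT assessments after randomisation, and the shift tables run to each scheduled visit. Section 10.2 describes affiliated laboratories using the central ranges, so the fixed limits do not prove that other results are dropped. The ALT endpoint in section 12.7.5 uses a central laboratory dataset, yet it models all scheduled post-baseline visits and lists fallback covariance structures as having fewer parameters. With two visits, unstructured, ARH(1) and CSH each have three, so that wording presumes more visits. The signed SAP prevails and is not in the combined document.

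Much of this stands. Country and affiliated laboratories may well count as central. The section 12.7.5 wording may be standard text, or may reflect sites that test centrally throughout. None of it gives site-local results a stated way in, and section 10.2 itself separates a site's local laboratory from a central one. The eDISH wording covers ALT only.

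A reader might infer that laboratory safety oversight is lost. The document does not support that. Section 10.2 requires clinically relevant abnormal values on the laboratory and comment CRF pages, section 11.1 makes clinically significant ones adverse events, and the medical monitor reviews safety data throughout. A reader might also infer a biased dose comparison. Allocation is randomised, blinded and stratified by country, and missed capture follows laboratory location, not arm. Lower counts are possible, but no between-arm bias is shown.

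**Conclusion.** The point holds for site-local results. On the text available, section 12.9.2 restricts its outputs to central-laboratory data while four of six scheduled on-treatment visits may be tested locally. Early transient rises could therefore be under-counted in the PCS, maximum-value and eDISH outputs.

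The size is uncertain. At a local-laboratory site, central values alone would see 15%, 31% or 46% of 4-, 8- or 12-week rises, against 38%, 62% or 85% with all results. Full central rechecking nearly closes that gap (35%, 60%, 83%). These figures rest on assumed durations, even onset and an unknown recheck rate, and the effect on the whole trial also depends on an unknown share of local sites. A reader might take 67% as the fraction of panels lost. It is a ceiling that needs every site to be local, which sits badly with the per-country laboratories in section 8.2.4.

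No efficacy test is affected by this point. Confidence is moderate, because the SAP of 26 January 2017 may already settle it. The change is still worth making before database lock.

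**What to change.** State in section 12.9.2 that all post-randomisation results, including site-local ones, enter the PCS incidence, denominators and listings, the maximum ALT, AST and bilirubin distribution, and eDISH. Express ULN-based criteria as multiples of the reporting laboratory's own ULN, using the ranges that section 10.2 already requires. Convert results to the SI units of the PCS table for absolute limits. Repeat these outputs with central values only.

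Keep the shift tables, normal-baseline incidence, means and box plots on central data, affiliated laboratories included. Baseline has no local option, so adding local results there would mix a change of laboratory with a true change.

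If the SAP of 26 January 2017 already pools local results, align section 12.9.2 with it.

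The cost is a few sentences, the repeated outputs, and a check that local values and ranges for weeks 2, 4, 8 and 40 are in the database. No visits or samples are added. The downside is some between-laboratory noise, which the central-only repeat makes visible.
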